8.1.3. Sensitivity Analyses

In addition to the conservative imputation for the US/FDA primary efficacy endpoint detailed in [Section 8.1.2](#), the following sensitivity analyses of the primary efficacy endpoint will be performed separately at 6, 12 and 36 months for the ITT population only.

- The primary outcome will be imputed exactly as in [Section 8.1.2](#) except that a subject imputed as having a recurrence because of missing data at Month 6 (or Month 12 or Month 36) for any reason will be considered as NOT having a recurrence. Inferential analysis employing the same methods as for the primary analysis will be performed.
- A “tipping point” analysis will be performed. This analysis will begin by using the following imputations associated with missing data at Month 6 (or Month 12 or Month 36) for any reason: FAI insert treated subjects will be considered as having a recurrence, and sham treated subjects will be considered as NOT having a recurrence. The analysis will proceed one imputed FAI insert treated subject at a time, assuming that this given subject will be considered as NOT having a recurrence. All other imputations stated in [Section 8.1.2](#) will be performed during this “tipping point” analysis. Inferential analysis employing the same methods as for the primary analysis will be performed at each step of the “tipping point” assessment.

Additionally, for missing data due to any reason, sensitivity analyses will be conducted by using multiple imputation (MI) methods. The list of subjects who will have their Month 6 (or 12 or 36) value imputed using MI methods will be determined prior to each database lock. A fully conditional specification (FCS) imputation method will be used to impute missing recurrence values. Five imputations will be performed to obtain five complete data sets. The volume of missing data will be assessed prior to unmasking at Month 6 and the number of imputations may be increased, if necessary. The SAS procedure MI will be used to generate the imputed data sets. The following variables will be included in the imputation model: recurrence, age, gender, treatment group, systemic treatment at study entry (stratification factor), duration of disease (years) in the study eye, number of recurrences in study eye within the 12 months prior to screening, and bilateral uveitis history (yes/no). The imputed datasets will be analyzed by a logistic regression model with recurrence as the dependent term and treatment as the independent term. Using the SAS procedure MIANALYZE, results from the logistic regression analysis of the five imputed data sets will be combined to obtain overall estimates [SAS/STAT User Guide, version 9.3]. Additional details are provided in [Appendix 13.2](#). Note: for this sensitivity analysis, subjects who have not previously experienced a recurrence and who take prohibited medications prior to the time point of interest will have their Month 6 (or 12 or 36) value imputed as a recurrence as described in [Section 8.1.2](#).

The primary efficacy endpoint will be also analyzed with logistic regression with recurrence as the dependent term and treatment as the independent term, and including systemic treatment at study entry (stratification factor) as a covariate.¹

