4.1. Sample Size

A two group continuity corrected Chi-square test with a 0.05 two-sided significance level will have 89% power to detect the difference between a Sham group recurrence free rate of 0.600 and a FAI treated group recurrence free rate of 0.880 (odds ratio of 0.205) when the sample sizes are 40 and 80, respectively (a total sample size of 120).

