4.2.1. Masking of Study Team

Prior to the Month 6 database lock, study team members at PPD and pSivida Corp. will be masked to the treatment assignments, with the exception of the PPD randomization team. After the Month 6 database lock, the PPD Biostatistics, Programming and Medical Writing team members and pSivida will become unmasked. The PPD Clinical and Data Management team members will remain masked to subject-level treatment assignments until after the Month 36 database lock.

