13.2 SAS Code for Multiple Imputation Method

A fully conditional specification (FCS) imputation method will be used to impute missing recurrence values at Month 6 (or 12 or 36). The following SAS code will be used to generate the imputed data sets:

```
PROC MI DATA = <derived dataset> SEED = xxxxxx NIMPUTE = 5;  
  CLASS NoRecurrence Gender TrtGroup StratFactor BilateralUveitis;  
  FCS DISCRIM (NoRecurrence Gender BilateralUveitis TrtGroup)  
    LOGISTIC (StratFactor/ ORDER=INTERNAL)  
    REG (Age DurDisease NumRecur);  
  VAR Age Gender DurDisease StratFactor NumRecur BilateralUveitis TrtGroup  
    NoRecurrence;  
RUN;
```

where

NoRecurrence indicates whether the subject completed through Month 6 (or 12 or 36) without a recurrence of uveitis in the study eye (1 = Yes, 0 = No),

Age is the subject's age in years,

BilateralUveitis indicates whether the subject has a history of bilateral uveitis (1 = Yes, 0 = No).

DurDisease is the duration of disease (years) in the study eye,

Gender (1 = Male, 2 = Female),

NumRecur is the number of recurrences in the study eye within the 12 months prior to Screening,

StratFactor indicates the use of systemic treatment at study entry (1 = Not receiving systemic treatment, 2 = Receiving systemic treatment – corticosteroid therapy, 3 = Receiving systemic treatment – immunosuppressive therapy),

TrtGroup is the treatment variable.

The following model will be fit in the SAS procedure LOGISTIC to analysis the imputed datasets:

```
Ods Output ParameterEstimates = parms CovB = covb;  
PROC LOGISTIC DATA = < MI dataset >  
  BY _IMPUTATION_ ;  
  CLASS NoRecurrence TrtGroup (REF=last) \ PARAM=ref;  
  MODEL NoRecurrence (event = '1') = TrtGroup/ covb;  
RUN;
```

Then the SAS procedure MIANALYZE will be used to obtain the overall estimates, using the ParameterEstimates and CovB ods output datasets from the LOGISTIC procedure. The following code will be used:

```
Ods Output ParameterEstimates = MIparms;  
PROC MIANALYZE PARMS(classvar=classval)= parms  
                  COVB (effectvar=stacking)= covb;  
  CLASS TrtGroup;  
  MODELEFFECTS intercept TrtGroup;  
RUN;
```

The odds ratio and 95% confidence interval will be calculated by taking the exponentiation of the ESTIMATE, LCLMean and UCLMean variables where PARM = 'TrtGroup' in the MIparms dataset. Variable Probt from the same observation will be used for the p-value.

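### Five imputations leave avoidable seed-to-seed variation in the supportive multiple-imputation analysis, and the option to use more has no criterion and is tied to Month 6 only

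*SAP*

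**What the plan says.** SAP 8.1.3 lists the sensitivity analyses of the primary endpoint, which "will be performed separately at 6, 12 and 36 months for the ITT population only". For MI it says "Five imputations will be performed to obtain five complete data sets", and then: "The volume of missing data will be assessed prior to unmasking at Month 6 and the number of imputations may be increased, if necessary". No threshold, target number or Monte Carlo error limit follows, and no matching review is described for Months 12 or 36. The same section does settle, before each database lock, which subjects will have values imputed.

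SAP 13.2 gives the code, with "SEED = xxxxxx NIMPUTE = 5". A logistic model is fitted to each completed data set and the results are pooled. The pooled odds ratio and 95% confidence interval are reported, and "Variable Probt from the same observation will be used for the p-value".

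On masking, SAP 4.2.1 says: "After the Month 6 database lock, the PPD Biostatistics, Programming and Medical Writing team members and pSivida will become unmasked".

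**The concern.** An MI estimate is an average over random draws, so it carries simulation error that shrinks as the number of imputations, m, grows. With m = 5 and about 120 binary outcomes, that error may be visible in the reported odds ratio and p-value. Two analysts running the same code with different seeds would then report different figures from the same data. The safeguard is discretionary and tied to Month 6. If missing data accumulate over follow-up, the error would be larger at the later analyses, for which no review of m is stated. At stake is the stability of one supportive result at each of three time points.

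**Working it through.** **1. The plan's own figure.** SAP 4.1 states: "A two group continuity corrected Chi-square test with a 0.05 two-sided significance level will have 89% power". Its inputs are recurrence-free rates of 0.600 (sham, n = 40) and 0.880 (FAI, n = 80), so d = 0.28 and r = 2.

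- Continuity correction: k = (r+1)/(r·d) = 1.5/0.28 = 5.357. Effective n = 40 − k + k²/(4·40) = 40 − 5.357 + 0.179 = 34.82.
- Mean rate = (0.600 + 2·0.880)/3 = 0.7867.
- z = [0.28·√34.82 − 1.96·√(1.5·0.7867·0.2133)] / √(0.24 + 0.1056/2) = (1.652 − 0.983)/0.541 = 1.236, giving power 0.892.
- Odds ratio = (0.6/0.4)/(0.88/0.12) = 0.2045.

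Both stated figures reproduce. The documents give no expected missing share and no Monte Carlo error, so those parts rest on assumptions.

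**2. Formula for the seed effect.** With mean within-imputation variance U and between-imputation variance B, the pooled variance is T = U + (1 + 1/m)B. Repeating the procedure with new seeds moves the pooled estimate with variance B/m. The seed SD as a fraction of the standard error is therefore about √(λ/m), where λ is roughly B/T. The simulated λ at m = 100 is 0.097 at 10% missing, 0.194 at 20% and 0.290 at 30%.

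- 10% missing: √(0.097/5) = 0.14; √(0.097/100) = 0.03.
- 25% missing (λ midway between the 20% and 30% values, 0.242): √(0.242/5) = 0.22; √(0.242/100) = 0.05.

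**3. Simulation.** The observed data are held fixed and only the seed varies. Each imputation draws an arm-specific rate from a Beta posterior (prior 0.5, 0.5) and then binomial outcomes. Log odds ratios are pooled by Rubin's rules with a t reference. The missing share is equal by arm. No covariates are used, because the documents give no covariate data. At rates near the planning values (20,000 seeds):

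| Missing (assumed) | Seed SD / SE, m = 5 | m = 50 | m = 100 | Seeds with p < 0.05, m = 5 |
|---|---|---|---|---|
| 5% | 0.10 | 0.03 | 0.02 | 100% |
| 10% | 0.14 | 0.04 | 0.03 | 100% |
| 20% | 0.19 | 0.06 | 0.04 | 99.8% |
| 30% | 0.23 | 0.08 | 0.05 | 93.7% |

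**4. Three worked cases** (5th–95th percentile over seeds; 20,000 seeds at m = 5, 3,000 at m = 100). Counts are recurrence-free among observed:

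- 10% missing, near planning rates (FAI 63/72, sham 22/36). m = 5: odds ratio 3.96–5.00, p 0.001–0.008, every seed below 0.05. m = 100: odds ratio 4.34–4.57, p 0.002–0.003.
- 10% missing, borderline (62/72 and 25/36). m = 5: p 0.024–0.083, 59% of seeds below 0.05. m = 100: p 0.038–0.050, 96% below.
- 25% missing, borderline (34/60 and 11/30). m = 5: p 0.03–0.20, 19% of seeds below 0.05. m = 100: p 0.06–0.09, fewer than 0.1% below.

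**5. The primary method on the same cases.** It counts missing as recurrence and uses the continuity-corrected chi-square, N(|ad − bc| − N/2)² / (product of the four margins).

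- 63/80 v 22/40: 120·700²/(80·40·85·35) = 6.18, p = 0.013.
- 62/80 v 25/40: 120·420²/(80·40·87·33) = 2.30, p = 0.129.
- 34/80 v 11/40: 120·420²/(80·40·45·75) = 1.96, p = 0.162.

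In both borderline cases the primary method is already non-significant.

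**The case against.** The strongest reply is that nothing decisive depends on this analysis. The primary test uses no seed. SAP 8.1.1 treats the Month 12 and 36 tests as supportive, with no type I error adjustment. In the borderline cases where the seed moves MI across 0.05, the primary method has failed anyway. All of this stands and limits the point to a minor one.

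The noise is also modest: 0.14² and 0.22² are about 2% and 5% of the variance, and Rubin's rules already include the 1/m term. That keeps the interval honest on average. It does not stop the reported figures from moving with the seed.

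The missing shares are assumed, and the 25% case is severe. Only subjects without a known recurrence are imputed, so that case has 10 of 21 such sham subjects (10 missing plus 11 observed recurrence-free) and 20 of 54 such FAI subjects without data. The SAP's covariate-based model would also shift the figures somewhat.

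Four stronger readings are tempting, and the documents do not support them:

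- **The blank seed causes the variation.** It does not. The cause is m = 5, and fixing a seed hides the noise without reducing it.
- **The seed will be picked after unmasking.** Nothing says so. The placeholder sits beside a placeholder data set name in template code.
- **MI is the only planned analysis that neither fixes missing outcomes nor steps through them.** The per-protocol analysis excludes subjects with an imputed endpoint (SAP 4.3.2) and receives the same test (SAP 8.1.1), with no simulation error.
- **The plan makes no provision for more imputations.** It does. The weakness is that the provision has no criterion and is tied to Month 6.

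**Conclusion.** The point holds as a minor, nearly cost-free improvement. With m = 5 the MI results carry seed-to-seed variation four to five times as large as with m = 100 (√(100/5) = 4.5). The absolute size depends on missing shares that are assumed here, and on an arm-only imputation model.

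At near-planning effects the 0.05 conclusion is the same for at least 99.8% of seeds up to 20% missing and for 93.7% at 30%. Seed-dependent significance needs a borderline result or heavy missing data. A reader might infer that the trial's conclusion could turn on the seed. The primary analysis and its power are unaffected, so that inference fails.

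**What to change.** In SAP 8.1.3 and 13.2, set the number of imputations to at least 100 for Months 6, 12 and 36. Keep the option to go higher, but replace the discretionary wording with a rule: raise m until the Monte Carlo error of the log odds ratio is below a stated fraction of its standard error. With a fraction of 0.05, for example, m must be at least λ/0.0025. That is 39 for λ = 0.097, so the floor of 100 applies, and 116 for λ = 0.290.

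Separately, for reproducibility and not to reduce noise, record the numeric seed before each remaining database lock, because biostatistics and the sponsor are unmasked after Month 6. SAP 11.2 already lists changes made after unmasking, so a change to the Month 6 analysis at this stage belongs in that list.

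The cost is a few words in two sections and negligible computing time. Subjects, sites and the primary test are not touched.

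### The multiple-imputation check predicts recurrence from arm and baseline variables only, by a discriminant function with no stated predictor list, so it overstates recurrence in the arms under non-informative drop-out, and the direction of its effect on the odds ratio is unsettled

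*SAP*

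**What the plan says.** SAP 8.1.3 describes the imputation model: "The following variables will be included in the imputation model: recurrence, age, gender, treatment group, systemic treatment at study entry (stratification factor"), and then "duration of disease (years) in the study eye, number of recurrences in study eye within the 12 months prior to screening, and bilateral uveitis history". The imputed data sets are analysed by a "logistic regression model with recurrence as the dependent term and treatment as the independent term", and Appendix 13.2 converts the estimate to an odds ratio for no recurrence.

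The code in Appendix 13.2 declares "CLASS NoRecurrence Gender TrtGroup StratFactor BilateralUveitis" and imputes the outcome through "FCS DISCRIM (NoRecurrence Gender BilateralUveitis TrtGroup"). The `VAR` statement carries the same variables as the text. No predictor list is given for `NoRecurrence`, and neither text nor code includes the time last seen, interim vitreous haze or interim BCVA.

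Two rules determine who is imputed:
- Under SAP 8.1.2, data count as missing only for a subject with no earlier recurrence. The reasons include discontinuation, a missed visit and a visit outside the window.
- Under SAP 8.1.3, recurrences assigned because of prohibited medication stay fixed as recurrences and are not imputed.

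The protocol schedules eye examinations at Days 7 and 28 and Months 2 and 3 before Month 6, so the unused information is collected. The same imputation is planned for Months 12 and 36.

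**The concern.** Every subject to be imputed who returned after Day 1 has some recurrence-free follow-up, and the model discards it. The risk assigned is that of subjects whose status is known. That group is itself enriched for recurrence, because a subject who recurs and then leaves is known, while one who leaves quiet is not. A subject examined and quiet just after Day 208, if on the imputation list, also draws a full-period risk although the assessment period is over.

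Separately, a discriminant function assumes roughly normal predictors within each outcome class, whereas arm, stratum, gender and bilateral history are categorical.

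What is at stake is the meaning of the only sensitivity analysis that models the missing outcomes. The others assign fixed values. If its bias can run either way according to an unstated coding detail, agreement or disagreement with the primary result is hard to interpret.

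**Working it through.** **Inputs.** SAP 4.1 gives "Sham group recurrence free rate of 0.600 and a FAI treated group recurrence free rate of 0.880 (odds ratio of 0.205"). The planned arms are 40 sham and 80 FAI subjects. Six-month recurrence risks are therefore F = 0.40 (sham) and 0.12 (FAI), and the odds ratio for no recurrence is (0.88/0.12)/(0.60/0.40) = 4.889. Drop-out rate, timing, mechanism and hazard shape are not in the documents. Assumed: 5-20% drop-out, equal in both arms, even over 6 months and non-informative; constant hazard, with a rising hazard (Weibull shape 2) as a variant.

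**1. The plan's own figure.** The SAP states: "A two group continuity corrected Chi-square test with a 0.05 two-sided significance level will have 89% power".
- With δ = 0.28, ratio r = 2 and pooled rate (0.60 + 2×0.88)/3 = 0.787, the uncorrected sham sample size at 89.2% power is [1.96√(0.787×0.213×1.5) + 1.237√(0.24 + 0.1056/2)]²/0.28² = 34.8.
- The correction (n/4)[1 + √(1 + 2(r+1)/(r·n·δ))]² gives 40.0.
- The stated 89% is reproduced, as is the odds ratio, 1/4.889 = 0.2045. The SAP gives no figure for the imputation analysis.

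**2. One subject last seen quiet at Month 3.** Residual risk is 1 − S(6)/S(3).
- Constant hazard: 1 − 0.6^0.5 = 0.225 in sham against 0.40 for the full period (excess 0.175); 0.062 in FAI against 0.12 (excess 0.058).
- Rising hazard: excesses of 0.082 and 0.029.

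**3. Arm-level effect of ignoring follow-up, treatment a logistic-type predictor.** Let H = −ln(1−F). The mean probability of being quiet at drop-out is E = F/H: 0.783 in sham, 0.939 in FAI. With drop-out d, the missing fraction is dE, known recurrences are F − d(E − (1−F)), and the known-status rate is their ratio to 1 − dE.
- At d = 0.15, sham: (0.40 − 0.15×0.183)/(1 − 0.117) = 0.422. True residual risk in the missing: 1 − 0.60/0.783 = 0.234.
- At d = 0.15, FAI: (0.12 − 0.15×0.0587)/(1 − 0.141) = 0.129. True residual risk in the missing: 0.063.

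| Drop-out | Sham estimate (excess, points) | FAI estimate (excess, points) | Odds ratio (true 4.889) |
|---|---|---|---|
| 5% | 40.7% (+0.7) | 12.3% (+0.3) | 4.897 |
| 10% | 41.4% (+1.4) | 12.6% (+0.6) | 4.905 |
| 15% | 42.2% (+2.2) | 12.9% (+0.9) | 4.914 |
| 20% | 43.1% (+3.1) | 13.3% (+1.3) | 4.923 |

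Under the rising hazard, computed the same way with E integrated numerically, the excess is 0.5-2.1 points in sham and 0.2-0.9 in FAI.

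**4. Discriminant step alone, arm the only predictor.**
- Share of FAI among non-recurrers: (2/3×0.88)/0.787 = 0.746. Among recurrers: (2/3×0.12)/0.213 = 0.375.
- Pooled within-class variance: 0.787×0.746×0.254 + 0.213×0.375×0.625 = 0.199.
- Slope: (0.746 − 0.375)/0.199 = 1.86, against a true log odds ratio of 1.59.
- Imputed recurrence: 0.435 in sham (true 0.40) and 0.107 in FAI (true 0.12).

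**5. Both together.** A large-sample simulation (200,000 sham, 400,000 FAI) gives, at 10% drop-out, recurrence of 0.418 and 0.124 and an odds ratio of 5.06 against 4.92 in the simulated truth. At 20% it is 5.15 against 4.90. Logistic imputation, still baseline only, gives 4.94 at 10%. Conditioning on time last seen gives 0.401, 0.120 and 4.92.

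**6. If arm did not act in the step.** At 15% drop-out the pooled known-status rate is (0.3725/3 + 2×0.1112/3)/(0.8825/3 + 2×0.8592/3) = 0.229.
- Sham: 0.3725 + 0.1175×0.229 = 0.399. FAI: 0.1112 + 0.1408×0.229 = 0.143.
- Difference 25.6 points against 28.0; odds ratio about 3.97.

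**7. Later time points.** If the same constant hazard continued to Month 36, a sham subject quiet to Month 30 would have 40% residual risk but draw 1 − 0.6⁶ = 95%. For FAI it would be 12% against 1 − 0.88⁶ = 54%.

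**The case against.** The strongest reply is that the planned estimate is an odds ratio, and on that scale ignoring follow-up barely matters. At 15% drop-out the log odds ratio moves by ln(4.914/4.889) = 0.005, against a standard error of √(1/24 + 1/16 + 1/70.4 + 1/9.6) = 0.47. This stands.

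It is also fair that the primary analysis counts every missing subject as a recurrence, that a tipping-point analysis starts from the case least favourable to FAI, and that few subjects will be imputed (about 0.117×40 = 5 in sham at 15% drop-out). The list of subjects to be imputed is set before each lock, so out-of-window cases could be left off it, although the SAP text covers data missing for any reason.

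A reader might infer that the check is biased in favour of FAI because recurrence is overstated more in sham. The documents do not support that as a fixed direction:
- The discriminant step by itself understates FAI recurrence; the FAI overstatement comes from ignoring follow-up.
- If arm did not act in the step, the bias would run against FAI.
- SAP 5.1 lists lack of efficacy among the discontinuation reasons. Such drop-outs could carry above-average residual risk, which would cancel or reverse the bias.

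Nor should one infer that treatment is left out of the model. The SAP text says it is included; the code simply does not settle how it enters.

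**Conclusion.** The point holds as a minor one. The imputation model omits recurrence-free follow-up and uses a discriminant function with categorical variables and no stated predictors for the outcome. Under non-informative drop-out this overstates recurrence in both arms when treatment is a logistic-type predictor, by the amounts tabulated, with little effect on the odds ratio. With arm as a predictor, the discriminant step causes most of the shift in the odds ratio, which is still small against its standard error: ln(5.06/4.92) = 0.03 at 10% drop-out. The larger possible distortion, ln(3.97/4.89) = −0.21 at 15%, arises only if arm does not act in the step.

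Drop-out rate, timing, mechanism and hazard shape are all assumptions, and the simulation speaks to large-sample bias, not to the imputation variance. The discarded follow-up grows at Months 12 and 36. The primary test is not affected.

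**What to change.** - Replace the discriminant method for `NoRecurrence` with logistic imputation, and write out its predictors, with treatment and stratum included.
- Condition on the time of the last recurrence-free examination, either by imputing interval by interval within arm or by adding time last seen to the model.
- Keep the predictor list short, because few subjects will be missing.
- Apply the same at Months 12 and 36.

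The cost is one SAP paragraph and revised code in Appendix 13.2. The drawback is that some intervals will be sparse, which may force wider intervals or fewer covariates.
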